1.2 STUDY DESIGN

This is a Phase III, placebo-controlled, double-blind, multicenter study to assess the efficacy, safety, antiviral activity, and pharmacokinetics of RO7496998 (AT-527) compared with placebo in non-hospitalized adult and adolescent patients with mild to moderate coronavirus disease 2019 (COVID-19) in the outpatient setting.

[figure not shown]
The study will enroll approximately 1386 patients (including approximately 100 adolescents, up to a maximum of 150, with the remaining patients being adults) with confirmed severe acute respiratory syndrome coronavirus (SARS-CoV-2) infection.

The study consists of two periods: a 5-day treatment period and a 28-day safety and efficacy follow-up period, with mandatory study visits on Days 1, 2, 3, 5, 7, and 14. Some of these visits may be conducted by mobile nursing or telemedicine. In addition to mandatory study visits, there will be telephone calls on Day 21 (± 2 days) and Day 28 (± 2 days). The end of study visit will take place on Day 33 (± 3 days), preferentially as a telephone consult but may be conducted in-person in some instances, such as if the patient is enrolling in a longer-term follow-up RO7496998 (AT-527) study. The total study duration for each patient will be approximately 33 days.

The primary analysis will be performed once the data from the last patient's last visit has been collected in the database and all data has been cleaned and verified.

The study schema is shown in [Figure 1](#).

Figure 1 Study Schema

Randomization to 2:1 ratio (active:placebo).

BID=twice a day; N=number of patients; R=randomization; SARS-CoV=severe acute respiratory syndrome coronavirus; TC=telephone call.

1.2.1 Treatment Assignment and Blinding

Patients will be randomly assigned to one of two treatment arms: RO7496998 (AT-527) or matching placebo. Randomization will occur in a 2:1 ratio of RO7496998 (AT-527) to placebo through use of a permuted-block randomization method to ensure a balanced assignment to each treatment arm. Randomization will be stratified by region (North America, Europe, and rest of the world [ROW]) and presence of a high-risk factor (yes, no) for hospitalization due to COVID-19 (see Protocol Sections 3.1 and 3.3.2 for details). A minimum of 40% of the overall study sample will have a high-risk factor for hospitalization because of COVID-19. A minimum of 40% will also be expected for the otherwise healthy population. Stratification caps will be implemented within interactive voice/Web-based response system (IxRS) to ensure these requirements are met.

Study site personnel and patients will be blinded to treatment assignment during the study. The Sponsor and its agents will also be blinded to treatment assignment, with the exception of individuals who require access to patient treatment assignments to fulfill their job roles during a clinical trial (see Protocol Sections 4.2.2 for details).

If unblinding is necessary for a medical emergency (e.g., in the case of a serious adverse event [SAE] for which patient management might be affected by knowledge of

treatment assignment), the investigator will be able to break the treatment code by contacting the IxRS.

As per health authority reporting requirements, the Sponsor's Drug Safety representative will break the treatment code for all serious, unexpected suspected adverse reactions (see Protocol Section 5.7) that are considered by the investigator or Sponsor to be related to an investigational medicinal product (IMP; defined in Protocol Section 4.3).

1.2.2 Sponsor Review and Adjudication

Sponsor representatives from clinical science who are independent of the study team will review data from the study for the purposes of adjudicating adverse events (AEs) identified by the investigator as COVID-19-related complications. This adjudication will determine medically confirmed COVID-19-related complications, which will be used for the frequency of COVID-19-related complications endpoint. These complications and the role and process of Sponsor review and adjudication will be specified in a separate charter.

1.2.3 Data Monitoring

An external independent Data Monitoring Committee (iDMC) will evaluate safety according to policies and procedures detailed in the iDMC charter.

If an interim analysis is conducted for efficacy, the Sponsor will remain blinded. The interim analysis will be conducted by an external statistical group and reviewed by the iDMC. Interactions between the iDMC and Sponsor will be carried out as specified in the iDMC charter.

2. STATISTICAL HYPOTHESES

2.1 PRIMARY ENDPOINT

The primary efficacy analysis for this study will evaluate the time to alleviation or improvement of COVID-19 symptoms maintained for a duration of 21.5 hours of RO7496998 (AT-527) compared with placebo to demonstrate superiority of RO7496998 (AT-527) over placebo.

Let $h_{AT-527}(t)$ be the hazard function for RO7496998 (AT-527) and $h_{PBO}(t)$ be the hazard function for placebo, then the statistical hypothesis tested at a two-sided 0.025 significance level is:

Null hypothesis: The hazard functions for the time to alleviation or improvement of COVID-19 symptoms maintained for a duration of 21.5 hours are the same for RO7496998 (AT-527) arm and placebo arm:

$$H_0: h_{AT-527}(t) = h_{PBO}(t)$$

Alternative hypothesis: The hazard functions for the time to alleviation or improvement of COVID-19 symptoms maintained for a duration of 21.5 hours are not the same for RO7496998 (AT-527) arm and placebo arm:

[figure not shown]
$$H_A: h_{AT-527}(t) \neq h_{PBO}(t)$$

2.2 MULTIPLICITY ADJUSTMENT

The primary and key secondary endpoints ([Figure 2](#)) will be evaluated in a hierarchical manner with multiplicity control via multistage gatekeeping under the truncated Holm multiple testing procedure ([Dmitrienko et al. 2008](#)). In Families 1 and 2 of key secondary endpoints, the same truncation parameter value of 0.7 will be applied; no truncation is applied in Family 3, since it is prioritized lowest in the hierarchy and imposes no gatekeeping restrictions on subsequent families. The truncation parameter and the relative effect sizes of the endpoints influence how power is balanced over the secondary endpoint families. Truncation parameter values close to 1 should generally be chosen when the effect sizes in high-priority endpoints are relatively large in order to maximize overall power. In other settings where the effect sizes might be smaller or mixed, a truncation parameter value closer to 0 could improve overall power. A parameter value strictly less than 1 in testing families that impose parallel gatekeeping (i.e., at least one endpoint is considered statistically significant after multiplicity adjustment in order to test the next family) is needed to achieve strong overall type I error control ([Dmitrienko et al. 2009](#)).

Under this multistage gatekeeping approach, multiplicity-adjusted p-values will reflect the gatekeeping restrictions depicted in [Figure 2](#). In particular, the adjusted p-values for all key secondary endpoints in Families 1, 2, and 3 will be no smaller than the p-value for the primary endpoint. Similarly, the smallest adjusted p-value in Family 2 (3) will be no smaller than the smallest adjusted p-value in Family 1 (2). Endpoints for which the multiplicity-adjusted p-value is greater than 0.025 will not be considered statistically significant. These endpoints and all endpoints not under multiplicity control will be considered to provide supportive information. By repeated application of Proposition 4.1 of [Dmitrienko et al. \(2008\)](#), this testing strategy ensures that the overall type I error is no greater than 2.5%.

Figure 2 Multiple Testing Procedure for Endpoints

Ordering of endpoints within a family will be based on the p-value results from the hypotheses tests of the endpoints

COVID-19=coronavirus disease 2019; RT-qPCR=reverse-transcriptase quantitative polymerase chain reaction; SARS-CoV-2=severe acute respiratory syndrome coronavirus-2.

3. SAMPLE SIZE DETERMINATION

The required sample size of the efficacy-evaluable set is 1248 patients. It is assumed that the reverse-transcriptase quantitative polymerase chain reaction (RT-qPCR) positive rate for SARS-CoV-2 will be 90%. Therefore, approximately 1386 patients will be randomized to ensure an adequate number of patients in the efficacy-evaluable set. The total number of randomized patients may change based on the percentage of patients who are RT-qPCR positive during the study.

Rationale for the Target Sample Size

The required sample size has been calculated to ensure at least 90% power to detect a hazard ratio of 1.25 in the TTAIS of COVID-19 between the RO7496998 (AT-527) group and the placebo group. This corresponds to a 2-day improvement in the median TTAIS, assuming a median in the placebo group of 10 days ([Regeneron 2020](#)). Patients will be randomized to a 2:1 ratio to RO7496998 (AT-527) or placebo, respectively, and the fixed follow-up period will be 29 days. The study will require 1248 patients in the efficacy-evaluable set based on an expected 90% event rate (1122 events required) in order for the log-rank test to have at least 90% power with a two-sided significance level of 0.025, under the assumption of an exponential distribution. Additional patients may be enrolled

AT-527—F. Hoffmann-La Roche Ltd. and Atea Pharmaceuticals, Inc.

Statistical Analysis Plan CV43043

in order to observe 1122 events, where an event is meeting the primary endpoint. The minimal detectable difference is a hazard ratio of approximately 1.15, which equates to a difference in medians of approximately 1.33 days under the assumption of a 10-day placebo response.

4. ANALYSIS SETS

The following analysis sets are defined:

Analysis Set	Definition
Efficacy-evaluable	All randomized patients who received at least one dose of study treatment and were centrally assessed as reverse transcriptase quantitative polymerase chain reaction (RT-qPCR) positive for SARS-CoV-2 (by nasopharyngeal swab) at any point during the study, with patients grouped according to randomized treatment.
All patients	All randomized patients, with patients grouped according to randomized treatment.
Safety-evaluable	All randomized patients who received at least one dose of study treatment, with patients grouped to placebo if all doses received were placebo and to AT-527 if at least one dose of AT-527 was received.
PK-evaluable	All randomized patients who received at least one dose of study treatment and have sufficient data to enable estimation of key parameters (e.g., maximum concentration [C_{max}] and minimum concentration [C_{min}]), with patients grouped according to treatment received.

PK=pharmacokinetic; RT-qPCR= reverse transcriptase quantitative polymerase chain reaction; SARS-CoV-2=severe acute respiratory syndrome coronavirus-2.

The efficacy-evaluable set will be used for the primary efficacy analysis. In addition to having been randomized, patients are also required to have received at least one dose of study treatment, so that patients who drop out of the study after randomization but prior to first dose of study treatment will not be included in the analysis. As this is a double-blind study, patients will not know their randomized treatment therefore this cannot influence their decision to take study treatment. Additionally, patients are also required to be centrally assessed as RT-qPCR positive for SARS-CoV-2 (by nasopharyngeal swab) at any point during the study. This cannot be required prior to randomization as this would extend the time between first symptom onset and first dose of study treatment.

In addition, data will be listed for patients who do not receive the treatment they are assigned to at any timepoint.

5. STATISTICAL ANALYSES

Estimands for the primary and secondary endpoints are presented in [Table 2](#).

5.1 GENERAL CONSIDERATION

All statistical tests will be performed at a 0.025 significance level using two-sided tests, unless otherwise noted. As specified in Section 2.2, key secondary endpoints for which the multiplicity-adjusted p-value is greater than 0.025 will not be considered statistically significant. These endpoints and all endpoints not under multiplicity control will be considered to provide supportive information.

Statistical tests will use stratification factors according to IxRS unless there is considerable imbalance in IxRS and electronic Case Report Form (eCRF) stratum classification. Stratification factors may need to be removed or have their levels combined so that low or zero counts in one stratum do not invalidate relevant statistical tests.

Unless otherwise specified, continuous variables will be summarized by using the number of non-missing observations, arithmetic mean, standard deviation (SD), median, minimum, and maximum values as summary statistics; categorical variables will be summarized by using the frequency count and the percentage of subjects in each category as summary statistics. Descriptive summaries will be tabulated by treatment group.

All efficacy and virology analyses will be performed on the efficacy-evaluable set, all patient disposition and study conduct analyses will be performed on the All Patients set, and all safety analyses will be performed on the safety-evaluable set, unless otherwise specified.

Missing data due to study withdrawal or lost to follow up will be handled as described in Table 2. Any other missing data will not be imputed unless otherwise specified in the specific section describing an endpoint.

Time to event secondary efficacy and virology endpoints will use the same statistical methods as used for the primary endpoint as described in Section 5.3.2, and will be measured in days unless otherwise stated.

For time to event efficacy endpoints, once the first instance of the criteria has been met at an assessment, assessments with endpoint data present prior to the assessment that demonstrates the criteria is maintained for the required duration (either ≥ 21.5 hours or ≥ 43 hours as appropriate), must also meet the criteria to meet the endpoint i.e., subsequent assessments after a patient first meets the criteria but prior to the assessment showing maintenance of that criteria for 21.5 hours (or 43 hours if appropriate) must also meet the criteria if there is non-missing data at these assessments.

In addition, for time to event efficacy endpoints, once the endpoint has been met, subsequent data for a patient that does not meet the efficacy criteria will not result in a

null endpoint. Due to this, these endpoints can also be thought of as the time to first instance of a maintained defined criteria (such as alleviation) where maintained here refers to the required duration.

Secondary efficacy and virology endpoints that evaluate proportion of patients will be analyzed using a Cochran-Mantel-Haenszel test adjusted by the stratification factors for region (North America, Europe, ROW) and high-risk factor (yes, no), unless stated otherwise. The proportion in each treatment arm together with the difference in proportions, odds ratio and accompanying 97.5% CIs will be presented along with the p-value.

Continuous secondary virology endpoints, such as change from baseline endpoints, will be analyzed using an analysis of covariance (ANCOVA) model with region (North America, Europe, and ROW), high-risk factor (yes, no) as stratification variables, and the baseline value of the studied measure as a covariate. The least squares mean (LSM) change and its standard error (SE) of means in each group, the difference between two groups in least squares mean (LSM change), SE, and 97.5% CI, and p-values will be presented. Additionally, descriptive summaries for the change from baseline will also be presented by treatment group.

Area under the concentration curve (AUC) for secondary and exploratory endpoints will be analyzed using the van Elteren test where AUC is calculated using the trapezoidal method. AUC of change from time 0 (t_0) to time K (t_k) is given by the formula:

$$\sum_{k=1}^K \frac{(y_k + y_{k-1})(t_k - t_{k-1})}{2},$$

where t_k (hours) represents the date of the k^{th} virus RNA (reverse-transcriptase polymerase chain reaction [RT-PCR]) assessment ($k = 0, \dots, K$) and y_k represents the \log_{10} value of the k^{th} virus RNA (RT-PCR) assessment. 24-hours of time will be converted into one day.

Descriptive summary statistics of the AUC will be presented for each treatment group along with the p-value from the van Elteren test.

All secondary virology endpoints will be evaluated on the nasopharyngeal swab samples. Additional descriptive analyses for saliva and serum samples will be performed on an exploratory basis for the secondary virology endpoints, as required.

The qualitative result of the SARS-CoV-2 reverse-transcriptase polymerase chain reaction (RT-PCR) test is determined using cycle threshold (Ct) values. If the qualitative result is positive, then an associated quantitative result is also provided. The quantitative result is either numerical or below the limit of quantification (BLQ). The limit of quantification (LOQ) for the virus RNA is 120 copies/ml. If the virus RNA sample has a

positive qualitative result, but a quantitative result BLQ, virus RNA will be imputed as LOQ – 1 (119 copies/mL). Negative qualitative samples will be imputed as LOQ/2 (60 copies/ml) before being transformed to the log10 scale.

Baseline is defined as the last available assessment prior to first dose of study treatment. For efficacy analyses, if there is no such assessment available then baseline can be up to 4 hours post first dose, with the earliest assessment used as baseline in the case of multiple assessments within this time.

Secondary safety endpoints and other AE analyses will be assessed through descriptive summaries of treatment-emergent adverse events unless otherwise stated. A treatment-emergent adverse event is defined as any new adverse event reported or any worsening of an existing condition on or after the first dose of study treatment. Data reported will include data from baseline up until the patient completes/discontinues from the study and including data from the early termination visit, if applicable. All verbatim adverse event terms will be mapped to Medical Dictionary for Regulatory Activities (MedDRA) Preferred Terms, and adverse event severity will be graded according to the NCI CTCAE v5.0 scale. Adverse events will be tabulated by system organ class (in decreasing order of overall incidence) and by MedDRA Preferred Term (in decreasing order of overall incidence), unless otherwise stated.

Data will be analyzed per the reported assessment; time windows will not be implemented unless otherwise specified.

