6.4.3 Secondary Virology Endpoints

The secondary virology endpoints for this study are as follows:

- Change from baseline in amount of SARS-CoV-2 virus RNA as measured by RT-qPCR at each timepoint
- Time to cessation of SARS-CoV-2 viral shedding as measured by RT-qPCR
- Proportion of patients positive for SARS-CoV-2 virus RNA by RT-qPCR at specified timepoints
- Area under the concentration curve (AUC) in the amount of SARS-CoV-2 virus RNA as measured by RT-qPCR

Continuous secondary virology endpoints, such as change from baseline endpoints, will be analyzed using an analysis of covariance (ANCOVA) model with region (North America, Europe, ROW), high-risk factor (yes, no) as stratification variables, and the baseline value of the studied measure as a covariate. The treatment group means, difference in means, along with 95% CI and p-value will be presented.

Time to event secondary virology endpoints will be analyzed using similar methods as specified for the primary endpoint. Patients who are lost to follow-up, who do not have a response, or who die will be censored at their last contact date or date of death, whichever is applicable. Kaplan-Meier plots, median time to response, 95% CIs, and p-values will be presented.

Frequency and proportion secondary virology endpoints will be analyzed using a Cochran-Mantel-Haenszel test adjusted by the stratification factors at baseline, region (North America, Europe, ROW) and high-risk factor (yes, no), unless stated otherwise. The proportions and difference in proportions, together with a 95% CI and p-values will be presented.

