Key Secondary: Proportion of patients with ≥ 1 COVID-19 related medically attended visit	Patients with ≥ 1 COVID-19 related medically attended visit through to study end (including early termination visits)	Treatment-policy strategy approach will be taken. Patients are followed, assessed and analyzed irrespective of their completion of the planned course of the study treatment and irrespective of rescue and concomitant therapy (contd.)	Composite strategy where patient considered as having the event if they die (contd.)	Difference in proportion of patients between treatments (contd.)	The outcome measure up to point of study withdrawal will be used (contd.)
Secondary: Proportion of patients with any post treatment infection	Patients with any post treatment infection through to study end (including early termination visits)		Not an intercurrent event as it is the outcome measure		
Key Secondary: Frequency (Proportion) of COVID-19 related complications (including hospitalizations and deaths)	Patients with a medically confirmed COVID-19 related complication through to study end (including early termination visits)				
Key Secondary: Proportion of patients with all-cause mortality	Patients with all-cause mortality through to study end (including early termination visits)				

Table 2 Estimands (cont.)

Endpoint	Variable or Outcome Measurement	Intercurrent Events		Population-Level Summary for the Variable	Handling of Missing Data
		Treatment Withdrawal/Rescue/Concomitant Medications	Death		
Secondary (Virology): Change from baseline in amount of SARS-CoV-2 virus RNA	Amount of SARS-CoV-2 virus RNA, as measured by RT-qPCR at Day 3, Day 5, Day 7 and Day 14	Treatment-policy strategy approach will be taken. Patients are followed, assessed and analyzed irrespective of their completion of the planned course of the study treatment and irrespective of rescue and concomitant therapy.	While on treatment approach where the outcome measure up to point of intercurrent event will be used	Difference in mean change from baseline between treatments	The outcome measure up to point of study withdrawal will be used
Secondary (Virology): AUC in amount of SARS-CoV-2 virus RNA	Amount of SARS-CoV-2 virus RNA, as measured by RT-qPCR to Day 14			AUC for each treatment	

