5.5.2 Exploratory Virology Endpoints

The exploratory virology endpoints for this study are as follows:

- Treatment-emergent amino acid substitutions in SARS-CoV-2 viral genes (such as *nsp12* and potentially other genes)
- Anti-SARS-CoV-2 antibody status/titer for neutralizing antibodies and anti-S antibodies at specified timepoints
- Change from baseline in amount of SARS-CoV-2 virus titer at each timepoint
- Time to cessation of SARS-CoV-2 viral shedding as measured by virus titer
- Proportion of patients with positive SARS-CoV-2 virus titer at specified timepoints
- AUC of SARS-CoV-2 virus titer
- Drug susceptibility in patients with evaluable virus at specified timepoints

Time to event, incidence, proportion and change from baseline endpoints will be analyzed using the same approach as described for secondary virology endpoints in Section 5.1.

Additional analyses adjusting by baseline amount of virus RNA may also be conducted. Other virology endpoints will be summarized descriptively.

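### The viral RNA AUC is mislabelled as an AUC of change, and its planned test makes no use of baseline viral load to gain precision

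*SAP*

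**What the plan says.** **Definition.** SAP 5.1 announces an "AUC of change from time 0" and then gives a trapezoidal sum of adjacent pairs y_k + y_(k-1). It defines y_k as the log10 "value of the k^{th} virus RNA (RT-PCR) assessment", with k running from 0, and never subtracts y_0. SAP Table 2 gives the variable for this endpoint as "Amount of SARS-CoV-2 virus RNA, as measured by RT-qPCR to Day 14". Protocol 6.4.3 names the endpoint as the AUC "in the amount of SARS-CoV-2 virus RNA as measured by RT-qPCR".

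**Test.** SAP 5.1 says that AUC "for secondary and exploratory endpoints will be analyzed using the van Elteren test where AUC is calculated using the trapezoidal method". That paragraph names no strata and no covariate. Elsewhere SAP 5.1 says that statistical tests use the IxRS stratification factors. Protocol 6.4.4, under exploratory virology, also assigns AUC endpoints to the van Elteren test.

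**Baseline adjustment.** Protocol 6.4.3 states: "Continuous secondary virology endpoints, such as change from baseline endpoints, will be analyzed using an analysis of covariance (ANCOVA) model with region", high-risk factor and "the baseline value of the studied measure as a covariate". For AUC, Protocol 6.4.4 allows extra analyses adjusted for baseline viral RNA and defers their details to the SAP. SAP 5.5.2 says only: "Additional analyses adjusting by baseline amount of virus RNA may also be conducted". It names no endpoint and no model.

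**Status.** SAP 5.4.3 places RNA AUC among the supportive secondary virology endpoints. SAP Appendix 1, which lists changes from the protocol, does not mention it.

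**The concern.** There are two separate problems.

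The first is the definition. A programmer who follows the words and one who follows the formula would produce different endpoints. The difference is not small, because a patient's starting level carries through the whole curve.

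The second is efficiency and pre-specification. Patients enter with different viral loads, and an AUC of the level inherits those differences. A test that takes no account of them treats explainable variation as noise. The data needed are already there, since y_0 is the first term of the AUC. The adjusted analysis that the protocol said the SAP would specify is left without a model, so its form could be settled after unblinding.

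**Working it through.** **The plan's own figures.** Neither document gives a power, SD, correlation or sample size for RNA AUC. The only sizing is for the primary endpoint. With hazard ratio 1.25, 2:1 allocation, two-sided 0.025 and 90% power, the Schoenfeld formula gives (2.2414 + 1.2816)² / [(2/3)(1/3)(ln 1.25)²] = 1122 events, as stated. It has no bearing on this point.

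**Step 1: label against formula.** RNA is measured at Day 1 before dosing and on Days 3, 5, 7 and 14. The intervals are 2, 2, 2 and 7 days, so the trapezoidal weights are 1, 2, 2, 4.5 and 3.5, which sum to 13. Hence

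AUC of change = AUC of level − 13 × y_0.

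Take two patients with the same changes from baseline (0, −1, −2, −2.5, −3 log10):

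- Starting at 7: 13 + 11 + 9.5 + 29.75 = 63.25 log10-days.
- Starting at 5: 9 + 7 + 5.5 + 15.75 = 37.25 log10-days.
- AUC of change: 63.25 − 91 = −27.75 and 37.25 − 65 = −27.75.

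The formula separates these patients by 26 log10-days; the label would call them identical. (The second patient's last value, 100 copies/mL, lies under the 120 copies/mL limit. The SAP's imputation at 119 or 60 would move that AUC by less than 1.)

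Baseline has direct weight 1/13 = 7.7% in the AUC of the level. It is therefore inside the measure but not adjusted for.

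**Step 2: precision.** Assume equal SD at every visit and equal correlation r between visits. Neither is in the documents, so r is varied from 0.2 to 0.8. In units of SD²:

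- Level: V_L = 41.5(1 − r) + 169r, where 41.5 is the sum of squared weights and 169 = 13².
- Level adjusted for baseline: V_A = V_L − (1 + 12r)².
- Change: V_C = 184.5(1 − r), since the baseline weight becomes 1 − 13 = −12.

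Under randomization all three estimate the same treatment difference, so variance ratios are patient-number ratios. At r = 0.5, V_L = 20.75 + 84.5 = 105.25, V_A = 105.25 − 49 = 56.25 and V_C = 92.25, giving ratios of 1.87 and 1.64. The power columns apply where the adjusted analysis would have 90% power at two-sided 0.025: power = Φ(3.523/√ratio − 2.241).

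| r | V_L/V_A | V_C/V_A | Power, level | Power, change |
|---|---|---|---|---|
| 0.2 | 1.21 | 2.66 | 83% | 47% |
| 0.3 | 1.36 | 2.20 | 78% | 55% |
| 0.4 | 1.57 | 1.88 | 72% | 63% |
| 0.5 | 1.87 | 1.64 | 63% | 70% |
| 0.6 | 2.32 | 1.45 | 53% | 75% |
| 0.7 | 3.08 | 1.31 | 41% | 80% |
| 0.8 | 4.61 | 1.18 | 27% | 84% |

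These figures compare means. A rank test used in both analyses carries about the same efficiency factor in each, so the ratios carry over approximately. They ignore the assay floor and missing visits.

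**Step 3: is AUC of change a remedy?** V_C = V_L when 143(1 − r) = 169r, that is r = 143/312 = 0.46. Below that, for example at 0.4 or lower, AUC of change is less precise than the AUC of the level. Baseline adjustment beats both at every r tried.

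**The case against.** A reader might infer that the SAP departed from the protocol by dropping an ANCOVA. The documents do not support that. Protocol 6.4.4 assigns AUC endpoints to the van Elteren test without limiting this to titer, and its next remarks on adjustment refer to viral RNA, although the only AUC listed in that section is for titer. The ANCOVA sentence in 6.4.3 has change-from-baseline endpoints in view, and an AUC that begins at baseline has no baseline value of its own. ANCOVA for RNA AUC is one possible reading of an ambiguous protocol.

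A reader might also say that baseline is discarded, or that the test is wholly unadjusted. Neither is right. Baseline enters as y_0, and van Elteren is a stratified test, with IxRS factors applying under SAP 5.1. Only adjustment for viral load is missing.

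Nor is the test biased. Under randomization a chance baseline imbalance is random error already reflected in the p-value, and SAP 5.7.2.2 would show such an imbalance. Baseline-adjusted antiviral evidence is planned elsewhere, by ANCOVA on change in RNA at Days 3, 5, 7 and 14. A rank test is also a sensible choice when negative samples are set to 60 copies/mL and positive but unquantifiable ones to 119.

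All of this stands, and it narrows the point. It does not answer the wrong label, the unspecified adjusted analysis or the avoidable loss of precision. Some patients may lack a usable nasopharyngeal baseline, but the AUC as defined also needs y_0, so adjustment excludes no patient for whom that AUC can be calculated.

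**Conclusion.** The point holds in limited form. The label is wrong: formula, endpoint name and Table 2 agree on the AUC of the level. The planned test leaves baseline viral load unadjusted, and the adjusted analysis that the protocol deferred to the SAP has no model there. No departure from protocol and no bias should be claimed.

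The cost is precision. Leaving out baseline requires about 1.2 to 4.6 times the patients across the assumed correlations of 0.2 to 0.8. The direction is the same throughout that range, but the size depends on a correlation structure that the documents do not give. RNA AUC is supportive and outside multiplicity control, so no confirmatory conclusion depends on it. The change is still worth making, because it uses data already collected.

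**What to change.** Amend the SAP before unblinding:

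1. In 5.1, delete *of change* from the AUC definition.
2. State one main analysis for RNA AUC: a van Elteren test stratified by region and high-risk factor, applied to residuals from a regression of AUC on baseline log10 RNA, with treatment left out of that regression. Ranked AUC could replace AUC in the regression, but the SAP should name one of the two. This keeps the rank approach suited to the 60/119 copies/mL floor.
3. Report the van Elteren test without viral-load adjustment, with the same strata named, as supportive.
4. Replace the open-ended sentence in 5.5.2, as far as it concerns RNA AUC, with a reference to this analysis, and record the choice in Appendix 1.

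Do not switch to AUC of change alone.

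The cost is SAP wording and minor programming, with no new data, visits or patients.
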